### **Statistical analysis:**

Analysis was conducted using Statistical Product and Service Solution (SPSS) 25.0 (IBM Corp., USA), with a significance level set at 0.05. Descriptive statistics were used for demographic data analysis of participants, chi-square tests were employed for categorical variables, and independent samples t-tests were utilized for comparing differences between the two groups for continuous variables.

For motion analysis, kinetics, muscle activities, and motor control score percentages, independent samples t-tests were employed to compare the differences between the two groups.

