In summary, patellar tendinopathy may be associated with changes in landing patterns. However, the biomechanical alterations of the hip and knee joints in the frontal and transverse planes are still unclear. Furthermore, factors affecting movement patterns, such as movement control and muscle activation status, remain to be elucidated. Therefore, the purpose of this study is to investigate movement control in athletes with patellar tendinopathy and the biomechanical characteristics of the hip and knee joints during landing tasks. We hypothesize that athletes with PT symptoms will demonstrate poorer movement control abilities compared to those without

symptoms, and during the landing phase of loaded movements, they will exhibit increased hip adduction, greater hip extension torque, higher quadriceps activation, delayed gluteal activation timing, and earlier rectus femoris activation timing.

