## **Study design and participants:**

This is a cross-sectional observational study. Participants aged 18 to 40 were recruited for the experiment. The symptomatic group was selected based on the following criteria, and then matched to find an asymptomatic group.

Inclusion criteria for the symptomatic group were:

- ✓ Experiencing anterior knee pain during loading activities for more than three months
- ✓ Pain localized only to the inferior pole of the patella
- ✓ Having participated in collegiate-level or higher volleyball/basketball-related sports training for at least two years
- ✓ Currently engaging in activities inducing knee pain for at least 90 minutes per week
- ✓ Scoring below 80 on the Chinese version of the Victorian Institute of Sport Assessment-patellar tendinopathy questionnaire (VISA-PCh).

Inclusion criteria for the asymptomatic group were:

- ✓ Having participated in collegiate-level or higher volleyball/basketball-related sports training for at least two years
- ✓ Currently engaging in related activities for more than 90 minutes per week
- ✓ Reporting no lower limb pain scores greater than 3 (on a scale of 10) in the past three months
- ✓ Scoring greater than or equal to 80 on the VISA-PCh questionnaire.

Any of the following conditions in either the symptomatic or asymptomatic group led to exclusion from recruitment:

- ✓ Undergoing relevant rehabilitation exercises for knee pain in the past three months
- ✓ Having other chronic lower limb pain issues
- ✓ Self-reporting pregnancy
- ✓ History of lower limb surgery or patellar tendon steroid injections
- ✓ Medical history of rheumatic, immune, or neurological systemic diseases.

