## **Study methods:**

Data on participants' gender, age, height, weight, exercise frequency and duration, years of sports experience, specific sports discipline, participation in highest-level competitions, history of lower limb injuries, and completion of the

Chinese version of the Victorian Institute of Sport Assessment-patellar tendinopathy

questionnaire were collected via cloud-based forms. Using this information, eligible

participants were screened, with the symptomatic group recruited first. Then,

individuals in the asymptomatic group were matched to the symptomatic group based

on gender, age ( $\pm 10\%$ ), height ( $\pm 10\%$ ), weight ( $\pm 10\%$ ), and sports discipline.

Before testing, researchers conducted a second screening to confirm eligibility. If eligible, researchers provided detailed explanations of the study procedures and purposes to participants, who then signed informed consent forms. Prior to testing, participants warmed up for 5 minutes. Testing was conducted in the following order:

Jump height testing: Participants wore athletic shoes and performed a vertical jump test, followed by stationary and spike jump tests. Each test was performed three times for practice and three times for formal testing. The average of the formal test results, minus the average fingertip reach height, yielded the jump height results.

Ankle dorsiflexion angle measurement: Participants stood facing a wall with hands on the wall for support. While maintaining a lunge position with the front heel on the ground, participants dorsiflexed the ankle to its maximum angle. The angle formed between a line segment from the tip of the fibula to 10 cm below the lateral malleolus and the horizontal line was measured. The angle measurement was performed three times for each foot, and the average was taken.

Motor control testing: four tests were performed to assess hip and knee joint control, including hip flexion control, internal rotation control, external rotation/abduction control, and hip adduction control. Each test was practiced three times and performed formally five times.

Loading testing: Participants performed countermovement jump, drop vertical jump, and step-down test to assess lower limb function. Each test was performed according to specific protocols.

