Muscle electromyography (EMG) data collection: EMG electrodes were placed on both gluteus maximus, biceps femoris, rectus femoris, vastus lateralis ,and participants performed maximal voluntary isometric contractions. Additionally, handheld dynamometry was used to measure hip extensor strength.

Finally, data processing and statistical analysis were performed to complete the experiment.

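### No deciding test is named for any landing hypothesis: each could be tested on several tasks, and quadriceps activation also on two muscles and two measures, at an unadjusted 0.05 with no exploratory label

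*Combined protocol and SAP*

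**What the plan says.** The Statistical analysis section sets one threshold, "with a significance level set at 0.05", and one method for every outcome family: "For motion analysis, kinetics, muscle activities, and motor control score percentages, independent samples t-tests were employed". It ranks no outcome, gives no adjustment or testing order, and does not call any result exploratory. Nor does any other section available to this review; the part before the background section was not available.

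The background section ends with six directional hypotheses. One concerns motor control: "athletes with PT symptoms will demonstrate poorer movement control abilities". The other five concern "during the landing phase of loaded movements", where "they will exhibit increased hip adduction, greater hip extension torque, higher quadriceps activation, delayed gluteal activation timing, and earlier rectus femoris activation timing".

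Study methods lists three loading tasks: "Participants performed countermovement jump, drop vertical jump, and step-down test". It also lists the muscles recorded: "EMG electrodes were placed on both gluteus maximus, biceps femoris, rectus femoris, vastus lateralis". Two of these four belong to the quadriceps (rectus femoris and vastus lateralis) and one is gluteal. Data analysis computes both an average and a maximum activation per muscle, plus an onset time. It reduces the motor-control tests to one percentage score.

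**The concern.** The background section tells a reader which variables the hypotheses concern, but not which test decides each landing hypothesis. Hip adduction, hip extension torque, gluteal onset and rectus femoris onset can each be tested on every task. Quadriceps activation can be tested on every task, in either muscle, by either measure. The 0.05 applies to each test, and nothing limits the error within a hypothesis or across the six.

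At stake is the meaning of a statement that a landing hypothesis was supported. If several eligible tests exist and the report rests on the one that crossed 0.05, the chance of false support exceeds the nominal level, and a reader cannot tell by how much. Motor control does not have this problem, because its single score leaves one test.

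**Working it through.** The plan states no sample size, power or family-wise error rate, so there is no figure of its own to reproduce. The check counts eligible tests and then asks what the count could do.

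**Step 1: count from the plan's own lists.** Let T be the number of tasks: 3 as listed, or 2 if the step-down is not a landing.

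| Hypothesis | Formula | T = 3 | T = 2 |
|---|---|---|---|
| Motor control | 1 score | 1 | 1 |
| Hip adduction | T | 3 | 2 |
| Hip extension torque | T | 3 | 2 |
| Quadriceps activation | T × 2 muscles × 2 measures | 12 | 8 |
| Gluteal onset | T | 3 | 2 |
| Rectus femoris onset | T | 3 | 2 |
| Total | 8T + 1 | 25 | 17 |

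The count takes one limb and one time point per variable, and reads hip adduction as a single quantity. The plan does not fix these for the landing variables, so the true count could be higher.

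**Step 2: chance of at least one false result in the predicted direction.** Assumptions: two-sided 0.05 (the plan does not state sidedness), no true difference on any variable, and normal test statistics with a common correlation ρ. One test errs in the predicted direction with probability 0.05/2 = 2.5%.

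- Independent tests: 1 − 0.975^k.
- Correlated tests: 1 − ∫ φ(u) · Φ[(1.96 − √ρ·u)/√(1 − ρ)]^k du, where φ and Φ are the standard normal density and distribution functions.

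| Tests k | Meaning | ρ = 0 | ρ = 0.7 | ρ = 0.8 |
|---|---|---|---|---|
| 1 | one fixed test | 2.5% | 2.5% | 2.5% |
| 2 | task-only hypothesis, two tasks | 4.9% | 4.2% | 3.9% |
| 3 | task-only hypothesis, three tasks | 7.3% | 5.5% | 4.9% |
| 8 | quadriceps, two tasks | 18.3% | 9.5% | 7.9% |
| 12 | quadriceps, three tasks | 26.2% | 11.6% | 9.3% |

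For example, with k = 3 and independence: 1 − 0.975³ = 0.073.

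The independence column is an upper bound for quadriceps. Average and maximum activation of one muscle, in the same people and on the same maximum-contraction scale, will be correlated. The range used for quadriceps is therefore ρ = 0.8 to 0.7. For the task-only hypotheses the whole range from ρ = 0.8 to 0 is quoted.

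**Step 3: across all hypotheses.** For 25 tests the same formulas give 46.9% at ρ = 0 (1 − 0.975²⁵) and 15.8% at ρ = 0.7. For six tests, one per hypothesis, they give 14.1% and 8.2%. Fixing one test per hypothesis therefore removes the excess within each hypothesis but leaves some error across the six.

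**Step 4: price of a shared error rate.** Holm over six compares the smallest p-value with 0.05/6 = 0.0083, a critical value of 2.638. A test with 80% power at 0.05 (assumed) has non-centrality 1.960 + 0.842 = 2.802. Its power at that first step is Φ(2.802 − 2.638) = 0.565, about 56%.

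**The case against.** **The decision rule is inferred.** Nowhere does the plan say that one significant combination is enough. Reporting every task and measure separately fits the text equally well. This stands: the percentages describe what the plan permits, not what the team has said it will do. The plan still does not say what would count as support.

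**Quadriceps is the worst case.** A reader might infer that 12 tests and 9% to 12% are typical of every landing hypothesis. They are not. The other four vary by task only, because one gluteal muscle is recorded and rectus femoris is named. Their rate is about twice the single-test 2.5%, but still near 5%.

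**The step-down may not count.** The hypotheses concern a landing phase, and Study methods does not say that the step-down includes one. The counts of 12 and 25 are therefore ceilings on this point; 8 and 17 are the alternatives.

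**The study is observational.** The plan says so: "This is a cross-sectional observational study". Whether six distinct hypotheses in such a study should share one error rate is a matter of judgement. A reader might infer that omitting a multiplicity adjustment is itself the error. The documents do not support that, since nothing in them commits the study to a family-wise claim. What remains is that directional hypotheses are paired with a significance threshold, with neither a deciding test nor an exploratory label.

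**Conclusion.** The concern holds in this limited form. The omission is plain from the available text and does not depend on any calculation: for the five landing hypotheses, no test is named as the one that decides.

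Its size is illustrative. If any one significant result in the predicted direction were taken as support, the chance of false support would be:

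- about 5% to 7% for a hypothesis tested on three tasks, or 4% to 5% on two (correlation 0.8 to 0);
- about 9% to 12% for quadriceps activation with 12 tests, or 8% to 10% with 8 (correlation 0.8 to 0.7);
- about 16% to 47% for at least one such result among 25 tests (common correlation 0.7 to 0), the upper end being a bound.

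The comparison is 2.5% for one fixed test. All of this rests on two-sided testing, no true differences, assumed correlations and an inferred decision rule. The figures do not show that any reported finding is false. The point deserves action because the remedy is cheap and decides what the study can claim.

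**What to change.** First establish whether results have been seen; the design, methods and analysis sections are written largely in the past tense.

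**If results have been seen:** report all tests performed, label the analysis exploratory, and give estimates with 95% intervals. Disclose any ordering of outcomes as post hoc, and do not describe a hypothesis as confirmed.

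**If results have not been seen:**

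1. Name one variable per hypothesis as the deciding test, and one task for each landing hypothesis. For quadriceps activation this includes the muscle and the measure.
2. Base claims of support on those six tests only.
3. State that 0.05 applies per hypothesis. If the team prefers a shared error rate, apply Holm across the six instead; this is optional.
4. Report every other variable as exploratory, with estimates and 95% intervals.

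**Cost:** no new data. The team must choose the deciding variables and amend the text, and some confirmatory wording is lost. If Holm is chosen, a test with an assumed 80% power at 0.05 falls to about 56% at the first step.
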